## **5.6 Adjuvant Temozolomide and Disulfiram Treatment**

Approximately 4-6 weeks after completion of RT with concurrent TMZ, adjuvant TMZ may be administered for 6 cycles. Dosage of each cycle is 150-200 mg/m^2 PO per day on Days 1-5 of every 28-day cycle. DSF will be administered at 500 mg PO daily continuously in combination with adjuvant TMZ for up to 6 cycles as established by our previous phase I study. The timing for DSF and Cu are same as in Section 5.7. Additional adjuvant TMZ beyond 6 cycles may be given at the discretion of the treating medical oncologist but not with DSF. Per standard clinical care, adjuvant TMZ is typically given in the evening before bedtime rather than in the morning. The timing of adjuvant TMZ will be established at the discretion of the treating medical oncologist. Tumor-treating fields or Optune device (Novocure) as per routine clinical care during adjuvant TMZ is permitted at the discretion of the treating physician.

During adjuvant TMZ, the patient should be assessed every 2 months as per routine clinical care; however, more frequent visits may be performed as per the treating physician. During adjuvant DSF with concurrent TMZ, if a patient develops disease progression and undergoes surgical resection of the GBM, a portion of the tissue removed during surgery and along with blood will be archived for future research purposes (please refer to Section 9.0).

## **5.7 Optional Preoperative Disulfiram before Salvage Surgery**

After completion of adjuvant DSF, patients should be followed every 2-3 months as per routine clinical care. If a patient develops recurrent tumor during follow-up and plans to undergo another resection, he/she may opt for an optional preoperative DSF study prior to salvage surgery. Patients who would like to participate in this optional portion of the study will be treated with a 5-day (+/- 2 days) lead-in with oral DSF and Cu. DSF should be taken as 250 mg per day approximately 1 hour after dinner in the evening, and Cu should be taken as 2mg TID with each meals. Patient should not take DSF or Cu on the day of the surgery and should complete the drug diary (Appendix E).

## **5.8 Disulfiram Dose Escalation Criteria**

The first patient will be treated at Dose Level 2 with 250 mg of DSF daily, and doses for subsequent patients will be provided at the time of registration based on the toxicity experience of the previous patients on study using the TITE-CRM method, as detailed in Section 13.3.

Dose Escalation Schedule	
Dose Level	Dose of Disulfiram
Level 1	125 mg PO daily
Level 2	250 mg PO daily
Level 3	375 mg PO daily
Level 4	500 mg PO daily

For patients enrolling in the expansion cohort, the dose of DSF during RT will be 250 mg/day.

## **5.9 Definition of MTD, DLT, Dose Escalation Criteria, and Toxicity, Response, and DLT Evaluations**

### **5.9.1 Definition of Maximum Tolerated Dose (MTD)**

The maximum tolerated dose (MTD) of DSF is defined as the dose level at which 20% of the cohort experience DLT within 18 weeks from start of RT (or 12 weeks from the end of RT if there is a delay in RT). MTD is assessed from the first dose of DSF in combination with TMZ and RT; patients will not be assessed for DLT during the pre-surgery period when they are receiving the lead-in doses of DSF.

### **5.9.2 Dose Limiting Toxicities (DLTs)**

A DLT is defined as a clinically significant adverse event or abnormal laboratory value assessed as unrelated to disease progression, intercurrent illness, or concomitant medications/TMZ/adjuvant DSF which occurs within 18 weeks following the first dose of DSF with RT+TMZ (corresponding to approximately 6 weeks during RT and 12 weeks after RT) and meets any of the following criteria (all toxicity will be graded using CTCAE version 4.0):

- Any delay in RT treatment > 14 days that is possibly, probably, or definitely related to DSF will be considered a DLT.
- Any adverse event that requires dose reduction or discontinuation of DSF during RT that is possibly, probably, or definitely related to DSF will be considered a DLT.
- Grade 4 neutropenia or thrombocytopenia.

Note: These dose limiting hematological toxicities are most likely due to TMZ and may be attributed to TMZ. However, as a conservative assessment of the ability to combine DSF with RT and TMZ, these toxicities will be counted as a DLT as they would prompt discontinuation of TMZ.

- Serum creatinine  $> 2.0 \times$  ULN
- Total bilirubin  $> 2.0 \times$  ULN; AST or ALT  $> 3.0 \times$  ULN
- Other grade 3 or grade 4 non-hematologic toxicity that is possibly, probably, or definitely related to DSF, with the following specific exceptions:
  - Grade 3 fatigue
  - Grade 3 arthralgias/myalgias
  - Grade 3 or 4 nausea, vomiting, or anorexia that does not require discontinuing RT or TMZ
  - Diarrhea that can be adequately managed with outpatient medication such as loperamide and does not require hospitalization

Headaches are frequent in the brain tumor population and are usually due to diffuse increased intracranial pressure or compression of pain-sensitive intracranial structures (example: dura). The oncologists participating in this study are experienced clinicians accustomed to evaluation of brain tumor patients with headaches. Each patient with a headache is approached individually with a systematic assessment as to the etiology of the pain. Appropriate tests may include vital signs, CT or MRI scans, or other investigations. If, in the opinion of the treating oncologist, the headache is due to DSF, then the toxicity will be graded as above, and if  $\geq$  grade 3, it will be defined as a DLT.

Seizures are also a common complication associated with brain tumors. As noted in the preceding paragraph each patient will be approached individually and assessment for the cause of the seizure will be performed. If, in the opinion of the treating oncologist, the seizure is due to DSF, then the toxicity will be graded, and if  $\geq$  3, it will be defined as a DLT.

### **5.9.3 Toxicity, Response, and DLT Evaluations**

All patients who receive at least one dose of DSF are evaluable for toxicity. However, patients have to receive the combination of DSF with RT+TMZ to be evaluable for DLT. Of note, DLT evaluation starts when patient starts DSF with RT and does not apply during the preoperative DSF administration. Patients who do not have at least one dose of DSF with RT+TMZ will not be evaluable for DLT and will be replaced.

## **5.10 General Concomitant Medication and Supportive Care Guidelines**

The following medications and procedures are prohibited during the study:

- Any antineoplastic therapy other than RT, temozolomide, and DSF, except for the tumor-treating fields or Optune device when used in conjunction with adjuvant temozolomide and DSF
- Any investigational therapy other than DSF

All other medical conditions or manifestations of the patient's malignancy should be treated at the discretion of the investigator in accordance with local community standards of medical care.

Patients should not drive, operate dangerous tools or machinery, or engage in any other potentially hazardous activity that requires full alertness and coordination if they experience sedation while enrolled in this study.

Patients are to be instructed to abstain from alcohol while enrolled in this study.

### **5.10.1 Nausea and Vomiting**

Prophylactic antiemetic therapy may be used in this study at the discretion of treating physician. Because of the potential of benzodiazepines to interact with DSF through the cytochrome P450 system, the use of benzodiazepines for antiemetic prophylaxis should be reserved for patients who cannot be satisfactorily managed otherwise.

### **5.10.2 Diarrhea**

Antidiarrheal medications will not be used prophylactically; however, patients will be instructed to take loperamide, 4 mg total, at the occurrence of the first loose stool and then 2 mg every 2 hours until they are diarrhea-free for at least 12 hours. During the night, patients may take 4 mg of loperamide every 4 hours. Fluid intake should be maintained to avoid dehydration.

### **5.10.3 Central Nervous System Effects**

In our previous experience with 500-1000 mg of DSF per day with adjuvant TMZ, significant neurological toxicities, including delirium/psychosis, ataxia, visual changes, peripheral neuropathy, were observed, especially at the 1000 mg dose. Early signs of those symptoms should be carefully monitored. Once other causes such as tumor progression are ruled out, dose reduction of DSF during adjuvant TMZ should be considered if the toxicity is grade 2 or greater. If symptoms are not improving with dose reduction, DSF should be discontinued. Patients whose symptoms are not considered immediately life-threatening should be carefully monitored. Each patient may be approached individually with a systematic

assessment to rule out other causes. Appropriate tests may include vital signs; CT or MRI scans or other investigations.

If the patient's level of consciousness is considered to be life-threatening, the patient should be hospitalized and necessary measures should be instituted to secure the airway, ventilation, and intravenous access.

#### **5.10.4 Management of Disulfiram-Alcohol Reaction**

Severe DSF reactions caused by the patient's ingestion of alcohol should lead to emergency evaluation and supportive measures to restore blood pressure. Other recommendations include: oxygen, carbogen (95% oxygen and 5% carbon dioxide), vitamin C intravenously in massive doses (1 g), and ephedrine sulfate. Antihistamines have also been used intravenously. Potassium levels should be monitored, particularly in patients on digitalis, since hypokalemia has been reported.

### **5.11 Women of Childbearing Potential**

Women of childbearing potential (defined as women with regular menses, women with amenorrhea, women with irregular cycles, women using a contraceptive method that precludes withdrawal bleeding, or women who have had a tubal ligation) are required to have a negative serum pregnancy test within 14 days prior to the first dose of the study treatment.

Female and male patients (along with their female partners) are required to use a method of acceptable contraception, including one barrier method, during participation in the study and for 4 months following the last dose of study treatment.

If a patient is suspected to be pregnant, study treatment should be immediately discontinued. In addition a positive urine test must be confirmed by a serum pregnancy test. If it is confirmed that the patient is not pregnant, the patient may resume treatment.

If a female patient or female partner of a male patient becomes pregnant during therapy or within 4 months after the last dose of study treatment, the investigator must be notified in order to facilitate outcome follow-up.

### **5.12 Duration of Therapy**

If at any time the constraints of this protocol are considered to be detrimental to the patient's health and/or the patient no longer wishes to continue protocol therapy, the protocol therapy should be discontinued and the reason(s) for discontinuation documented in the case report forms.

In the absence of treatment delays due to adverse events, DSF treatment may continue until completion of 6 cycles of adjuvant TMZ or in the event of following:

- Documented and confirmed disease progression
- Death
- Adverse event(s) that, in the judgment of the investigator, may cause severe or permanent harm or which rule out continuation of study drug
- General or specific changes in the patient's condition render the patient unacceptable for further treatment in the judgment of the investigator
- Suspected pregnancy
- Serious noncompliance with the study protocol
- Lost to follow-up
- Patient withdraws consent
- Investigator removes the patient from study
- The Siteman Cancer Center decides to close the study

### **5.13 Duration of Follow-up**

Patients are evaluated for adverse events for 30 days after the last dose of DSF or until death, whichever occurs first. Patients removed from study for unacceptable adverse events will be followed until resolution or stabilization of the adverse event. Follow-up after the conclusion of adjuvant TMZ + DSF will be per routine clinical care. Two years after the patient comes off study, the chart will be reviewed to collect data on progression and survival.

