### **7.4 Timeframe for Reporting Required Events**

Adverse events will be tracked until the last dose of DSF. However, DLTs will only be evaluated for 18 weeks from the first day of DSF with RT+TMZ or at least 12 weeks following the completion of RT in the event there is a delay/interruption of RT. All clinically or laboratory adverse events that are > grade 1 (excluding lymphopenia) will be collected.

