
#### **14.3.5 Sample Size for the Dose-expansion Phase**

To further explore the effect of the addition of DSF/Cu to standard chemoradiotherapy for the subset of GBM with *IDH/BRAF/NF1* mutations, we propose to add an expansion cohort to further confirm that the addition of DSF/Cu to chemoradiotherapy may be a promising strategy to treat GBM with these mutations. Given historical data for a cohort of GBM is not readily available, some assumptions are used to derive a historical control benchmark. GBM with *BRAF* or *NF1* mutations are not known to have different prognosis than typical *IDH*-wildtype GBM [81,82], with historical OS of approximately 30% at 2 years and 10% at 5 years [3,83,84]. Both *BRAF* and *NF1* mutations affect the RAS/MAPK pathway and can also occur in the same patient, thus we will combine both mutations into one molecular cohort. However, *IDH*-mutant GBM is known to have better OS than *IDH*-wildtype GBM, with 2 year OS of approximately 50% and 5 year OS of approximately 20% [85], so we will define the second molecular cohort by the presence of *IDH* mutation. Therefore, a cohort with equal proportion of *IDH*-mutant GBM and *BRAF/NF1*-mutant GBM should theoretically have 2 year OS of 40% and 5-year OS of 15%. Based on such assumptions, a sample size of 24 patients (including 12 with *IDH* mutations and 12 with *BRAF/NF1* mutations) would provide 80% power with one-sided alpha of 0.10 to detect an improvement of 2-year OS from historical 40% to 60% (or a hazard ratio of 0.55). Since we have already enrolled 9 patients with these mutations (6 with *IDH* mutation, 2 with *BRAF* mutation, and 1 with *NF1* mutation), only additional 15 patients will be needed: 6 with *IDH* mutation, 9 patients with *BRAF* and/or *NF1* mutations. For the dose-expansion phase, patients are considered evaluable if a patient has received at least 4 weeks of DSF with RT, at either the MTD (375mg/day) or the RP2D (250mg/day). Inevaluable patients will be replaced.

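### Section 7.4 ends adverse-event tracking at the last disulfiram dose, while section 5.13 and both study calendars continue it for 30 more days

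*Combined protocol and SAP*

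**What the plan says.** Section 5.13 (Duration of Follow-up): "Patients are evaluated for adverse events for 30 days after the last dose of DSF or until death, whichever occurs first". The follow-up footnotes of both study calendars (10.1 footnote 16, 10.2 footnote 3) give the same 30 days, and the expansion calendar marks adverse events in its follow-up column.

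Section 7.4 (Timeframe for Reporting Required Events): "Adverse events will be tracked until the last dose of DSF". Its next sentence puts DLTs on a separate clock of 18 weeks from the first day of DSF with RT and temozolomide (TMZ), or "at least 12 weeks following the completion of RT in the event there is a delay/interruption of RT". It then defines what is recorded: "All clinically or laboratory adverse events that are > grade 1 (excluding lymphopenia) will be collected".

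Section 5.9.2 describes the 18-week DLT window as "corresponding to approximately 6 weeks during RT and 12 weeks after RT". Section 5.9.3 sets the safety population: "All patients who receive at least one dose of DSF are evaluable for toxicity". In the expansion phase, section 14.3.5 says "patients are considered evaluable if a patient has received at least 4 weeks of DSF with RT". Adjuvant treatment is optional: under section 5.6, "adjuvant TMZ may be administered for 6 cycles". Section 14.4 tabulates adverse events by type and grade.

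**The concern.** The first secondary objective is to describe the toxicity of DSF given with RT and TMZ, and the table in section 14.4 is its only analysis. If the collection period is not unique, the content of that table depends on which section the site staff follow, and practice could differ from patient to patient. The days after the last dose are not empty. Section 1.2.6 reports that in the previous phase I study the DSF-related toxicities were self-limiting or resolved within 30 days of stopping, so effects of the drug can plausibly still be seen in that interval.

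There is a related design question. Both clocks start from DSF, although the objective concerns the combination with RT. Section 14.3.1 justifies the TITE-CRM by noting that RT toxicity can appear months after treatment. No minimum time after RT is set for general adverse events. Patients who stop DSF early stay in the same safety denominator as completers but may be observed for much less time.

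**Working it through.** **Inputs**

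- End of general collection: last DSF dose (section 7.4), or 30 days later, 30/7 = 4.29 weeks (section 5.13; 10.1 footnote 16; 10.2 footnote 3).
- RT lasts 6 weeks (10.1 footnote 15). The DLT window runs to 12 weeks after RT (section 5.9.2).
- Adjuvant treatment starts 4–6 weeks after RT, for six 28-day cycles (section 5.6; 10.2 footnote 2).
- New expansion patients: 15 (section 14.3.5).

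**The plan's own figures.** DLT window: 6 + 12 = 18 weeks, as stated. Study duration: 6 + 4 + 6 × 4 = 34 weeks, which agrees with section 14.3.4 (36 weeks if adjuvant treatment starts 6 weeks after RT). Both reproduce.

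**The conflict.** For a completer, the last DSF dose falls at week 34–36. General collection then ends at week 34–36 under section 7.4, or at 34 + 4.29 = 38.3 to 36 + 4.29 = 40.3 under section 5.13. The disputed interval is 30 days for any patient, whenever DSF stops. For 15 patients it is 15 × 30 = 450 patient-days, or 450/7 = 64 patient-weeks. Deaths within the interval would reduce this. Inevaluable patients who are replaced but remain in the safety set would add to it.

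**Early stoppers without adjuvant therapy.** Let *s* be the week of the last DSF dose. Under the 30-day rule, the distance from the end of general collection to week 18 is 18 − (*s* + 30/7).

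- *s* = 6 (last day of RT): 18 − 10.29 = 7.7 weeks.
- *s* = 4 (the minimum DSF exposure in section 14.3.5): 18 − 8.29 = 9.7 weeks.

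Under section 7.4 as written, the distances are 18 − 6 = 12 and 18 − 4 = 14 weeks. For *s* = 4, however, the weekly review during RT and TMZ (10.2 footnote 15) would probably carry observation to about week 6. So 7.7 weeks is the smallest distance under the 30-day rule, and earlier stops give larger ones.

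**Completers for comparison.** Collection ends 34 − 6 = 28 to 36 − 6 = 30 weeks after RT under section 7.4, and about 32–34 weeks after RT under section 5.13. They are followed well past week 18 under either rule.

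**What the DLT clock picks up meanwhile.** Between the end of general collection and week 18, DLT-qualifying events are still evaluated. The criterion based on reducing or stopping DSF applies only during RT, and most remaining non-laboratory, non-haematological criteria need grade 3 or 4, with listed exemptions. New grade 2 events and exempt grade 3 events have no stated route into the table.

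**The case against.** On the conflict, the best defence is that section 7.4 is a single outlying sentence. Section 5.13 and two calendar footnotes say 30 days, so staff working from the calendar would do the right thing. It could also be said that section 7.4 concerns reporting rather than collection. The first argument shows which rule was probably meant, and so which sentence to correct. It does not remove the contradiction. The second fails because the same section states which events will be collected.

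On the period after RT, the defence is stronger. A reader might infer that the plan misses its own toxicity horizon, or that DLTs go unobserved once DSF stops. The documents support neither. The 12-weeks-after-RT window is defined for DLTs only, and section 7.4 deliberately separates the two clocks. Section 14.3.4 follows patients for DLT from the start of treatment to 18 weeks, whether or not DSF continues. Under section 6.2, a DSF-related event that requires dose reduction during RT is already a DLT. Section 5.13 also follows patients removed for unacceptable events until resolution or stabilization.

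Nor does every patient who stops DSF drop out of review. In the expansion calendar, footnote 15 gives 8-weekly adverse-event review during adjuvant TMZ without requiring that DSF continues. The escalation calendar (footnote 9) does impose that condition in cycles 3–6. The group in question is therefore limited to patients with no adjuvant therapy at all. Many of them may have progressed or died, and later events in them would be hard to separate from tumour or salvage treatment.

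What stands is that a 30-day, drug-anchored period is a defensible choice, and a longer one is a recommendation.

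**Conclusion.** Section 7.4 is wrong as written: it contradicts section 5.13 and both calendars on when adverse-event collection ends. The effect is confined to the secondary toxicity table, where events 1–30 days after the last DSF dose are in or out depending on the section followed. That is up to 450 patient-days among the 15 new expansion patients, ignoring deaths. How many events fall in that interval cannot be said from the documents. The MTD and overall survival analyses are untouched.

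The lack of a minimum period after RT is a secondary point and not an error. It concerns patients who stop DSF by the end of RT and receive no adjuvant therapy. Under the 30-day rule, their general collection ends at least 7.7 weeks before week 18. Their number cannot be derived. The 13% who did not complete concurrent TMZ in the study cited in section 1.1 is not a usable anchor, because it measures neither stopping DSF nor going without adjuvant therapy. No percentage of lost follow-up should be attached to this point.

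**What to change.** **Correction.** In section 7.4, replace the end of tracking with 30 days after the last DSF dose, or death if earlier, to match section 5.13 and the calendars. Leave the separate DLT clock as it is. The cost is one sentence. For the escalation patients, the report should state which rule was applied.

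**Recommendation, at the sponsor's discretion.** In sections 5.13 and 7.4 and the expansion calendar, collect adverse events until the later of 30 days after the last DSF dose and 12 weeks after the end of RT, whether or not the patient is still on DSF. The cost is one adverse-event check at 12 weeks after RT in what is likely to be a few patients. Some of the added events will be confounded by progression or salvage therapy, so the table should mark events that occur after progression.

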## **6.0 DOSE MODIFICATIONS**

### **6.1 Temozolomide Dose Modifications during Radiation Therapy**

No dose reduction will be made, but delay or discontinuation of TMZ administration will be decided weekly according to hematologic and non-hematologic adverse events, as specified below. Additionally, TMZ can be held at the discretion of the treating physician. If the administration of TMZ has to be interrupted, RT will proceed normally. Missed doses of TMZ will not be made up at the end of RT. The total number of days and total dose of temozolomide will be recorded on the patient's medication diary (Appendix C).

If one or more of the following are observed:

- ANC  $< 1.5 \times 10^9/\text{L}$  (Grade 2)
- Platelet count  $< 75 \times 10^9/\text{L}$  (Grade 2)
- Grade 3 non-hematologic AE (except alopecia, nausea and vomiting while on maximal antiemetic therapy, and fatigue)

Then treatment with concurrent TMZ will be withheld until all of the following conditions are met:

- ANC  $\geq 1.5 \times 10^9/L$
- Platelet count  $\geq 75 \times 10^9/L$
- Grade  $\leq 1$  non-hematologic AE (except alopecia, nausea and vomiting, and fatigue)

In case of hematologic AE as defined above, a complete blood count (CBC) should be performed at least weekly. In case of non-hematologic AE, the patient should be assessed at least weekly with relevant laboratory test(s). As soon as all of the above conditions are met, the administration of temozolomide will resume at the same dose as used initially.

If one or more of the following are observed:

- ANC  $< 0.5 \times 10^9/L$  (Grade 4)
- Platelet count  $< 25 \times 10^9/L$  (Grade 4)
- Grade 4 non-hematologic AE (except alopecia, nausea and vomiting unless the patient has failed maximal antiemetic therapy, and fatigue)

Then treatment with concurrent temozolomide should be discontinued.

AE	Value	Action
Grade 3 neutropenia	$\geq 0.5$ and $< 1.0 \times 10^9/L$	Hold TMZ until --ANC $\geq 1.5 \times 10^9/L$
Grade 2-3 thrombocytopenia	$\geq 25$ and $< 75 \times 10^9/L$	--Platelet $\geq 75 \times 10^9/L$
Grade 3 non-hematologic (except alopecia, nausea/vomiting unless on maximal antiemetic therapy)	NA	--Grade $\leq 1$ non- hematologic AE
Grade 4 neutropenia	$< 0.5 \times 10^9/L$	Stop TMZ
Grade 4 thrombocytopenia	$< 25 \times 10^9/L$	
Grade 4 non-hematologic (except alopecia, nausea/vomiting)	NA	

If RT has to be temporarily interrupted for technical or medical reasons unrelated to TMZ, then treatment with daily TMZ should continue. If RT has to be permanently discontinued then TMZ should stop until it is re-initiated at the adjuvant phase of treatment.

